Protocol for the clinical validation of a valgus knee brace for gonarthrosis

Presented to the Véritas IRB Research Ethics Committee

TOPMED

Version 02

Approved in French on March 27th 2023

Translated on June 25th 2025

NCT05814471

SCHEDULED START AND END DATES

From March 2023 to March 2024

RESEARCH PROJECT DESCRIPTION

Issues

Valgus knee braces (VKB) is one form of treatment to help patients suffering from gonarthrosis. The aim of this form of treatment is to compensate for certain biomechanical deficits in patients. A multitude of joint arrangements are available to target specific biomechanical deficits. A constant challenge for orthosis manufacturers is to transmit the biomechanical effect of the orthosis to the patient. The desired effect requires a change in the forces applied inside the knee, but the orthosis cannot directly transmit the forces to the patient's bones due to its external nature. Orthotic customization is essential to improve the transmission of the biomechanical effect, as well as tolerance to it. Comfort, ease of fitting and effectiveness are essential components a quality orthosis. With this in mind, Laboratoires Victhom Inc. would like to test its new knee brace attachment system.

State of knowledge and project relevance

There are 2 main types of orthosis for gonarthrosis: soft and rigid. Soft orthoses use malleable materials such as fabric or rubber to apply forces to the leg, while rigid orthoses use plastic or metal braces. What's more, three main types of fastening system are used on these types of orthoses: velcro, hybrid and cable-tied. Different configurations are therefore used to compensate for the biomechanical deficits attributable to the pathology.

Each fastening system has its advantages and disadvantages. Velcro fasteners are quick and intuitive to use, but there are a number of issues that come up when using them: adjustment difficulties, cleaning the system, the number of straps needed to hold the leg in position, and the noise produced when the velcro is released. Hybrid systems regularly contain velcro fasteners, to which quick-release fasteners have been added to simplify strap installation and removal. However, they retain most of the disadvantages of velcro systems. Cable tightening systems also feature quick-release fasteners. The advantage of cable clamping is that belts can be adjusted easily and precisely, with minimal noise.

The essential components of a quality orthosis are comfort, efficiency and ease of fitting. Comfort is paramount, as it is directly related patient adherence to treatment. The effectiveness of orthotic treatment can be measured by a reduction in gonarthrosis symptoms or medication use, and potentially an increase in the patient's ability to perform problematic movements. The ease with which the orthosis can be fitted is a component that needs to be optimized, as the user-friendliness of the treatment is important to increase patient adherence to it. The system developed in partnership with Laboratoires Victhom for this project is designed to simplify orthosis fitting, while maintaining comfort and effectiveness.

Research objectives

The aim of this research is to compare two fastening systems for VKB, one consisting of Velcro straps and the other of 3D-printed straps with cable clamping.

With this research, we seek to answer the following questions:

- Is the new cable-tightened belt system as effective at controlling symptoms as the Velcro fastening system currently on the market?
- Is the new cable-tightened strap system more comfortable than the Velcro fastening system currently on the market?
- Does the new fastening system make it easier to install the brace than the one currently on the market?

Our hypotheses are that the new attachment system will be more comfortable and easier to install than the one currently on the market.

Financing

The project was funded by NSERC's *Strengthening College and Community Innovation* program in partnership with Laboratoire Victhom Inc.

Partner company

Laboratoire Victhom Inc.

[name], Vice-President, Research and Development

[name]

[contact]

[contact]

RESEARCH METHODOLOGY

Research location

On TOPMED's premises at [name], Collège Mérici, Quebec City. Impression taking, orthosis delivery and adjustments prior to the trial period will be carried out at the balance clinic ([name]).

Type of test

Repeated measurements on single-factor groups with crossover: Attachment system (2 conditions).

Measurement, assessment and data collection tools

Logbook :

An electronic diary will be completed each day for the duration of wear of each orthotic condition. The diary will detail total wearing time, as well as sitting time, physical and sporting activities performed during the day, number of orthosis removals and adjustments, discomfort experienced and medication taken.

Questionnaires :

A questionnaire containing general information: age, sex, height, weight, whether they wear a knee brace on both legs, and the length of time since they purchased their personal brace. This questionnaire will be completed at the first trial meeting.

A subjective questionnaire (Satisfaction) will be completed by participants to assess the ease with which they put on and take off the brace, and to validate the comfort, fit and aesthetic appearance of the brace. This questionnaire will be completed 5 or 6 times, depending on the order of the participant's conditions.

A Quebec version of the Knee injury and Osteoarthritis Outcome Score (KOOS) questionnaire will be used to quantify the evolution of the participant's symptoms and their effects on quality of life. This questionnaire will be completed 4 times (delivery meeting and trial meetings 1 to 3).

A Quebec version of the Psychological Symptoms Inventory (Ilfeld 1976), abbreviated ISP hereafter, will be used to quantify the evolution of participants' psychological symptoms. This questionnaire will be completed 4 times (delivery session and trial sessions 1 to 3)

At each session, participants showing a clinically significant interpretation of their total score, anxiety (questions 2, 3, 9, 11, 13, 15, 16, 20, 22, 23, 29), depression (questions 1, 5, 6, 8, 10, 14, 18, 19, 21, 24), hostility (questions 12, 25, 26, 27) or concentration (questions 4, 7, 17, 18) will be contacted by e-mail to offer them mental health resources. Participants who chose an answer other than "never" to question 24 will also receive this e-mail. Links to these resources can also be found at the end of the questionnaire.

A fastening system comparison questionnaire will be completed at Trial 3 to ascertain participants' preferences regarding the installation and de-installation process, as well as their orthotics.

Photos of the fitted leg wearing the orthosis will be taken 5 or 6 times, depending on the order of the participant's conditions.

Estimated duration of participants' activities

A new knee brace will be made for each participant. To this end, an impression and anthropometric measurements will be taken during the first meeting with the participant to obtain an orthosis fitted to the patient's leg. Once the orthosis has been assembled, the participant will return to the balance clinic to receive his or her new orthosis. In addition, 3 questionnaires will be completed (ISP + KOOS + PAd1 Satisfaction) and photos of the fitted leg will be taken

Following the delivery meeting, a 14-day wearing period begins. Each time the brace is adjusted at the participant's request, the counter for the adjustment period is reset to zero. This wearing period will always be performed using the Velcro fastening system currently available on the market.

Once the fitting period is over, the first trial meeting will take place(d1). The 1st attachment system (C1) will be installed on the participant's orthosis. The order of attachment system conditions is randomized for participants. In addition, 4 questionnaires will be completed (General Info + ISP + KOOS + PAd14

Satisfaction). A 5th questionnaire (Satisfaction C1j1) will be added if the participant's first trial condition is the cable-tightening attachment system. This questionnaire will be completed after a few minutes' wear of the brace. Photographs of the fitted leg will be taken with all brace systems used during the trial. Following the first trial meeting, the first 14-day trial period begins. During this period, the participant must fill in an electronic logbook on a daily basis.

When the first trial period is over, the second trial takes place (d14). The 1st attachment system(C1) is removed and the 2nd system(C2) is installed on the participant's orthosis. In addition, 4 questionnaires are completed (ISP + KOOS + Satisfaction C1d14 + Satisfaction C2d14). Photos of the fitted leg will be taken, with all attachment systems used during the session. Following this meeting, the second 14-day trial period begins. Again for this period, the participant will be required to complete an electronic logbook on a daily basis.

The third and final trial meeting will take place following the 2nd trial period. The brace will be collected during this meeting. In addition, 4 questionnaires will be completed (ISP + KOOS + C2d28 Satisfaction + Attachment System Comparison). Photos of the fitted leg will be taken during the meeting.

Impression appointment: 45-minute appointment at the clinic.

Delivery meeting: 1 hour 45 minutes at the clinic. 3 questionnaires will be completed and photos of the fitted leg will be taken.

Adjustment meeting(s): These meetings are optional, will be held at the client's request and last a maximum of 45 minutes.

1st trial session: This session lasts 2 hours at TOPMED. If no change is made to the brace attachment system, 4 questionnaires will be completed. However, if the brace attachment system is changed during the session, 5 questionnaires will be completed. Photographs of the fitted leg will be taken.

2nd trial meeting: This meeting lasts 2 hours at TOPMED, with 4 completed questionnaires and verification of logbooks. Photos of the fitted leg will be taken.

3rd trial meeting: This meeting lasts 1 hour at TOPMED, with 4 completed questionnaires and verification of logbooks. Photos of the fitted leg will be taken. The orthosis will be picked up during this meeting.

PARTICIPATION OF LIVE HUMAN, ANIMAL OR MATERIAL PARTICIPANTS

10 adult participants will be recruited to test the different orthoses. Participants should have mainly worn an ODRA 2.0 orthosis to allow a shorter orthosis fitting period . Participants with lower-limb wounds should be excluded, as wearing the orthosis could aggravate these.

Participant inclusion criteria:

- Be 18 years of age or older;
- Have worn an ODRA 2.0 orthosis for an average of several hours a day over the past 6 months

Participant exclusion criteria:

- People with wounds on the lower limbs.

SCIENTIFIC JUSTIFICATION FOR USING LIVE SUBJECTS

The participation of human participants representative of the clientele is essential for the validation of the new cable-tightening fastening system. Participant feedback will provide us with essential information on the brace's ease of installation, comfort and symptom control, enabling us to confirm the desired properties and, if necessary, modify certain aspects to better match the needs and problems of the target clientele. In addition, the new attachment system needs to be tested on participants to measure the potential biomechanical effects of this new technology

RECRUITMENT

Vichom Laboratories will contact identified customers to request their consent to share their personal information with the research team. If consent is obtained, the customer's full name and e-mail address will be transferred to TOPMED. These consenting customers will then be contacted by TOPMED with an offer to participate in the current project. Candidates may express their interest by writing to TOPMED. A member of the project team ([name]/[name]/[name], Orthotics-Prosthetics Research Professional) will be available to answer questions, assess eligibility, send documentation and/or set up a telephone appointment at a later date.

RISKS AND DRAWBACKS, AND PROPOSED MITIGATION MEASURES

An allergic skin reaction (redness) due to wearing the brace is a potential injury. The participant should stop wearing the brace, if necessary.

Bruises, corns, scratches and/or pain may appear on the fitted limb, due to poor orthotic fit or incorrect positioning. The orthotist will be present to ensure the best possible fit of the orthosis during the session. Injuries due to appliance breakage are possible.

ADVANTAGES AND BENEFITS

No immediate benefit for participants, except the benefit of trying a new orthosis that could improve their quality of life. The advantage of their participation is that it will provide empirical data on orthosis wear. This is an advantage for Laboratoire Vichom Inc.

FREE AND INFORMED CONSENT

The Information and Consent Form (ICF) will be e-mailed to them once the candidate has shown interest by contacting us again. A period of two (2) weeks will be allowed for reading and reflection. Upon receipt of the signed CIF, the first meeting will be scheduled.

Participants may terminate their participation at any time without negative consequences or prejudice and without having to justify their decision. In this case, participants must inform the responsible researcher or a member of the research team. Thereafter, all material allowing the identification of the participant and the data provided will be destroyed, unless the participant authorizes the researcher to use them for the research despite the withdrawal. In this case, they will be preserved according to the measures described below, which will be applied to all other participants.

CONFIDENTIALITY AND PROTECTION OF PERSONAL INFORMATION

Information collected from questionnaires, photos, logs, anthropometric measurements, videos and gait

pattern analysis data is confidential and will be used only for the purposes of this research project, unless otherwise agreed by the participant. All data collected, notes, photos and computer recordings are encrypted on servers. Unless required by law, no information that could directly or indirectly reveal your identity will be disseminated or published without your prior explicit consent.

All questionnaires and digital logs have been created using the Lime Survey platform. The information processed is hosted in Canada on the platform's encrypted servers (Secure Socket Layer procedure), which comply with the RGPD standard.

Data will be stored in coded form for a period of five (5) years, then anonymized in a database for retention for a period of ten (10) years for statistical reference purposes.

CONTINUOUS EXAMINATION

Should any inconvenience arise following the completion of the prototype validation test, participants will be promptly notified.

DISSEMINATING RESULTS

No disclosure to patients will be made following the trials.

Results will not be published.

COMPENSATION

If necessary, a parking sticker will be provided to participants during their visit. A compensation of \$50 will be given for their participation in each meeting of the validation protocol. The total amount awarded may not exceed \$350, equivalent to the full protocol with 2 adjustment meetings. The first payment will be made after the first trial meeting. The remainder of the amount will be distributed at the last meeting or when the participant chooses to end his or her participation.

RESPONSIBILITY

The legal rights of each participant will be maintained.

PROTOCOL SEQUENCE

First contact

Email to candidates

- *0241_VICD_Courriel_Recruitment*

Admission

Demonstrate interest by responding to e-mail/phone call

Sending documents and explanations :

- *0241_VICD_CourrielFIC*
- *0241_VICD_Consent_form*

Receipt of signed consent

Telephone contact for impression appointment

COVID call

Self-evaluation confirmation 24 hours before each meeting.

Impression meeting

45-minute meeting at the balance clinic

Anthropometric measurements of the thigh and digital impression taken

Delivery meeting

Meeting at the Balanced Clinic 1h45

Questionnaires: Satisfaction + KOOS + ISP

- *0241_VICD_Questionnaire_Satisfaction*
- *0241_VICD_Questionnaire_KOOS*
- *0241_VICD_Questionnaire_ISP*

Photos

Adjustment meeting

These meetings are optional and will be held at the client's request at the balance clinic. They last a maximum of 45 minutes.

1st trial meeting

2-hour meeting on TOPMED premises

Logbook explanations

- *0241_VICD_JdB*

Questionnaires: KOOS + ISP + 2 Satisfaction questionnaires (one for the end of the adjustment phase, if condition 1 is different from the adjustment phase, a second comfort questionnaire is filled in)+ general information

- *0241_VICD_Questionnaire_Satisfaction*
- *0241_VICD_Questionnaire_KOOS*
- *0241_VICD_Questionnaire_ISP*
- *0241_VICD_General_Questionnaire*

Photos

2nd trial meeting

2-hour meeting on TOPMED premises

Checking logbooks

- *0241_VICD_JdB*

Questionnaires: KOOS + ISP + 2 Satisfaction questionnaires (one for the end of condition 1, another for the beginning of condition 2)

- *0241_VICD_Questionnaire_Satisfaction*
- *0241_VICD_Questionnaire_KOOS*
- *0241_VICD_Questionnaire_ISP*

Photos

3rd trial meeting

1-hour meeting on TOPMED premises

Checking logbooks

- *0241_VICD_JdB*

Questionnaires: KOOS + ISP + 1 Satisfaction questionnaires for the end of condition 2

- *0241_VICD_Questionnaire_Satisfaction*
- *0241_VICD_Questionnaire_KOOS*
- *0241_VICD_Questionnaire_ISP*
- *0241_VICD_Questionnaire_Comparison*

Photos

Data processing

Data recording: Questionnaires and logbooks

BIBLIOGRAPHY

Ilfeld, F. W. (1976). Further validation of a psychiatric symptom index in a normal population. *Psychological Reports*, 39(3, Pt 2), 1215-1228. <https://doi.org/10.2466/pr0.1976.39.3f.1215>

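### Does the question whether the cable system controls symptoms as well as Velcro need a hypothesis, a deciding measure and a margin in the protocol?

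*Protocol*

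**What the plan says.** Research objectives poses three questions. The first is "Is the new cable-tightened belt system as effective at controlling symptoms as the Velcro fastening system currently on the market"; the other two ask about comfort and ease of installation. The hypotheses follow: "Our hypotheses are that the new attachment system will be more comfortable and easier to install than the one currently on the market". None is stated for symptom control.

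State of knowledge and project relevance says "The effectiveness of orthotic treatment can be measured by a reduction in gonarthrosis symptoms or medication use", adds the ability to perform difficult movements as a possible further yardstick, and describes the device as "designed to simplify orthosis fitting, while maintaining comfort and effectiveness".

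Measurement, assessment and data collection tools gives each instrument a purpose:

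- The diary records, among other things, "number of orthosis removals and adjustments, discomfort experienced and medication taken".
- The Satisfaction questionnaire serves "to assess the ease with which they put on and take off the brace, and to validate the comfort", along with fit and appearance.
- "A Quebec version of the Knee injury and Osteoarthritis Outcome Score (KOOS) questionnaire will be used to quantify the evolution" of participants' symptoms and what those symptoms do to quality of life.

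Scientific justification for using live subjects says feedback will inform on ease of installation, "comfort and symptom control, enabling us to confirm the desired properties and, if necessary, modify certain aspects". Ten adults are planned.

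**The concern.** Symptom control is the only one of the three questions about clinical effect and the only one worded as no difference, yet it alone has no hypothesis. The background section joins its yardsticks for effectiveness with an *or*, and KOOS, diary discomfort and diary medication are all collected. These could disagree: a participant might hold KOOS steady by taking more medication. If nothing says which one decides, being as effective has no fixed meaning.

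The justification section then speaks of confirming the desired properties, and the background lists maintained effectiveness as a design aim. Read together, these could be taken as a promise to confirm no loss of symptom control in 10 people. The risk is that a non-significant difference in so small a sample is reported as equal effectiveness, and that an easier fastening is accepted although it costs some symptom control.

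**Working it through.** **1. Is a measure assigned?** No instrument is tied to a numbered question anywhere in the protocol. Each is linked by its stated purpose.

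| Question | Instrument by stated purpose | Other relevant data |
|---|---|---|
| Symptom control | KOOS | Diary medication and discomfort |
| Comfort | Satisfaction | Diary discomfort |
| Ease of installation | Satisfaction | Comparison questionnaire at trial meeting 3 |

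The link from KOOS to symptoms is as explicit as the link from Satisfaction to comfort and ease. All three questions have more than one relevant source and none names a deciding one, so symptom control is not singled out.

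**2. Is it measured at the right time?** Estimated duration of participants' activities places KOOS at delivery and at trial meetings 1 to 3. Meeting 2 closes the first 14-day condition and meeting 3 closes the second. A within-person cable-minus-Velcro difference is therefore available without extra data.

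**3. What does the wording on confirmation promise?** It sits in the rationale for involving human participants. The same sentence foresees changing aspects of the device if needed, which is the language of prototype feedback. The no-loss reading arises only by joining it to a description of design intent in another section.

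**4. What can 10 participants show?** The protocol's only figure is 10. It states no alpha, power, standard deviation or margin, so 10 cannot be reproduced. The rest of this step is an illustration on assumed margins. The unit is the SD of the within-person difference, with a two-sided 95% interval, true difference zero and, where a period term is fitted, equal numbers in each order.

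- Half-width = t(0.975, df)/√n.
  - n = 10, 9 df: 2.262/3.162 = 0.715 SD.
  - n = 10, 8 df (period term): 2.306/3.162 = 0.729 SD.
  - n = 8 (assumed losses), 7 df: 2.365/2.828 = 0.836 SD.
- The chance that the interval excludes a loss of m is the probability that a noncentral t with noncentrality m√n exceeds t(0.975, df). For n = 10:

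| Margin m (SD) | m√10 | 9 df | 8 df |
|---|---|---|---|
| 0.50 | 1.58 | 29% | 29% |
| 0.75 | 2.37 | 56% | 55% |
| 1.00 | 3.16 | 80% | 79% |

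- The margin giving 80% power is 0.996 SD (9 df) or 1.012 SD (8 df). With 8 completers and 7 df it is 1.156 SD.
- On a 0–100 score with an assumed SD of 10, 15 or 20 points, the half-width for 10 completers is 7.2, 10.7 or 14.3 points.

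The trial could reliably rule out only a loss of about one SD of the difference. That describes a small study; it does not conflict with any power statement, because the protocol makes none.

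**The case for a change.** The best case for a change is that objectives and hypotheses are protocol content, so an unseen analysis plan does not excuse a question left without a hypothesis. The choice between symptoms, medication and function settles what the question means and is more than an analytical detail. Two or three sentences would settle it, with no added visits or questionnaires, and would guard against reading a non-significant difference as equality.

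Part of this stands. There is no hypothesis and no criterion for symptom control, KOOS is not ranked against medication use, and *confirm* is a strong verb for 10 people. But a research question may be asked without a predicted answer, and leaving this one without a hypothesis fits a descriptive aim and contradicts nothing. The question asks about controlling symptoms, and KOOS is the instrument described as quantifying them. An analyst would take the KOOS difference between conditions with its interval and treat diary medication as supportive. The KOOS score to use, any margin and the method are commonly left to the analysis plan. Replacing *confirm* with *estimate* would read better, but it corrects no rule.

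**Conclusion.** No change to the plan is called for. The claim that symptom control lacks an assigned measure, unlike comfort and ease, does not hold: KOOS is linked to symptoms by purpose and is scheduled at the end of each condition. What survives is missing detail and one loosely worded sentence in a small prototype test whose results, according to Disseminating results, will not be published.

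The arithmetic is sound as illustration: a half-width of about 0.72 SD with 10 completers, and 80% power only for margins near 1.0 SD. It rests on assumed margins and a true difference of zero, and the SD itself is unknown. Its practical message concerns interpretation: report the difference with its interval, and do not take a non-significant result as evidence of equal effectiveness. Nothing in the protocol requires the opposite. If the analysis plan, once seen, proved to declare equal effectiveness from a non-significant test, that would be a separate and more serious point.

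### Can question 1, on symptom control, be answered when no KOOS score or medication record is taken without the brace?

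*Protocol*

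**What the plan says.** Under Research objectives the Protocol sets out to compare a Velcro and a cable fastening on a valgus knee brace. It asks three questions, the first being "Is the new cable-tightened belt system as effective at controlling symptoms as the Velcro fastening system currently on the market". The stated hypotheses concern only the other two: "Our hypotheses are that the new attachment system will be more comfortable and easier to install than the one currently on the market".

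In the background (State of knowledge and project relevance) it remarks: "The effectiveness of orthotic treatment can be measured by a reduction in gonarthrosis symptoms or medication use". The sentence goes on to mention a possible gain in the ability to perform difficult movements.

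The data available for question 1 are fixed as follows:

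- **Population** (Participant inclusion criteria): "Have worn an ODRA 2.0 orthosis for an average of several hours a day over the past 6 months".
- **KOOS** (Measurement, assessment and data collection tools): "This questionnaire will be completed 4 times (delivery meeting and trial meetings 1 to 3".
- **Run-in** (Estimated duration of participants' activities): 14 days from delivery of the new brace, restarted after each requested adjustment. "This wearing period will always be performed using the Velcro fastening system currently available on the market".
- **Diary** (Measurement, assessment and data collection tools): "An electronic diary will be completed each day for the duration of wear of each orthotic condition". It records medication, wearing time, removals and adjustments. Under Protocol sequence it is first explained at the 1st trial meeting.
- **Sample size**: "10 adult participants will be recruited to test the different orthoses".

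**The concern.** If effectiveness means a reduction in symptoms or medication, there has to be a level from which the reduction is taken. The schedule contains none. Participants arrive after six months of brace wear, and every KOOS score reflects some form of brace use. The only medication record begins with the first trial condition.

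Two equal KOOS means would then fit two quite different situations: both fastenings control symptoms, or neither does. This matters more for question 1 than for the other two. Where the hypothesis is superiority (comfort, ease of fitting), an insensitive measure works against the new system. Where the question is whether the new system is no worse, anything that pulls the scores together looks like success. The stated purpose of the new system includes keeping the brace's effectiveness, and one might say this cannot be judged without first showing that there was an effect to keep. Nor could any analysis recover a reference that was never collected.

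**Working it through.** **1. What each measurement reflects** (Estimated duration of participants' activities; Protocol sequence).

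| Time point | KOOS | State it reflects | Diary covers the preceding period? |
|---|---|---|---|
| Delivery | yes | habitual wear of the earlier brace | no |
| Trial meeting 1 | yes | at least 14 days of Velcro on the new brace | no |
| Trial meeting 2 | yes | 14 days of condition 1 | yes |
| Trial meeting 3 | yes | 14 days of condition 2 | yes |

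The count is 1 + 3 = 4 KOOS administrations, which agrees with the Protocol. Off-brace scores: 0 of 4. Diary: 14 + 14 = 28 days out of at least 14 + 14 + 14 = 42 days on the new brace. The factual premise is correct.

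**2. Does the missing reference damage the comparison that is asked for?** For one participant let u be the unbraced level, b the benefit common to both fastenings, and e_c and e_v the remaining terms under cable and Velcro. Then

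cable − Velcro = (u + b + e_c) − (u + b + e_v) = e_c − e_v.

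Both u and b drop out. A paired simulation confirms this (n = 10, 100,000 replicates, assumed residual SD of 7 per condition). For b = 0, 10 and 20 the mean contrast was 0.00 with SD 3.1, and 95.0% of results were non-significant in each case. The theoretical SD is 7 × √2 / √10 = 3.13.

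This cuts both ways. Equal scores say nothing about b, and not knowing b does not bias the contrast. The diary covers both conditions for the same 14 days, so the medication contrast is balanced too.

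**3. Precision.** The Protocol gives no SD, margin or power, so the SDs below are assumptions. With 8 degrees of freedom (period effect fitted):

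half-width = t(0.975; 8) × SD / √10 = 2.306 / 3.162 × SD = 0.729 SD (0.715 SD with 9 degrees of freedom).

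| Assumed SD of difference | 95% half-width (points) | As % of an assumed 10-point brace benefit |
|---|---|---|
| 8 | 5.8 | 58% |
| 10 | 7.3 | 73% |
| 12 | 8.8 | 88% |
| 15 | 10.9 | 109% |

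For an assumed benefit of 5 points the range is 117% to 219%; for 15 points it is 39% to 73%. The half-width contains only n, SD and the t quantile. An off-brace KOOS would leave it unchanged, so these figures measure the consequence of having 10 participants, not of lacking a reference.

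**4. Would a favourable answer come too easily?** Only if a non-significant difference were read as equality, and the Protocol states no such rule. Under a margin rule (one-sided 2.5%, no true difference) the power to exclude a 5-point loss is 41%, 29%, 21% and 15% for SDs of 8, 10, 12 and 15. A favourable answer would then be hard to reach. The margin and decision rule commonly sit in a statistical analysis plan, which is not at hand.

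**5. What would the possible changes deliver?**

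- Rewording question 1 as a KOOS difference alters no data and no result.
- Starting the diary at delivery adds at least 14 days, all on Velcro. These give no unbraced reference and do not enter the condition 1 versus condition 2 contrast.
- An unbraced rating during a task at a trial meeting shows an immediate effect only. It supplies neither a KOOS nor a medication reference.

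**The case for a change.** The strongest case for a change is that the gap lies in data collection, so no later analysis can close it. The Protocol does not state that the Velcro brace's benefit is taken as given, and its single bibliography entry concerns a psychiatric symptom index, so no evidence of that benefit is cited. The brace is newly made for each participant, so past benefit from a personal brace is not a measurement of this one. A claim that effectiveness has been kept would then rest on something unobserved.

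The logical part of this stands: similar scores are not proof that either fastening controls symptoms. The rest is weaker. The question names the marketed Velcro system as its yardstick, and whether bracing works at all is not among the three questions. The remark about reductions is background on orthotic treatment in general. It says how effectiveness can be measured and does not define a trial endpoint, so the schedule does not contradict it. An unbraced arm would test the brace, whereas the trial swaps only the fastening on the same orthosis. Habitual wearers were chosen for a stated reason, a shorter fitting period. Low wear, offered as one way to obtain equal scores, would be visible in the diary, which records wearing time every day in both conditions.

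**Conclusion.** No change follows. The schedule has no off-brace or pre-brace reference, so question 1 can be answered only as a relative comparison in established brace wearers: the cable-minus-Velcro difference in end-of-period KOOS and in diary medication. That is what the question asks, and the randomised crossover provides it without depending on the size of the brace's own effect.

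The uncertainty is large: a half-width of 0.729 SD, or 5.8 to 10.9 points for assumed SDs of 8 to 15. It stems from having 10 participants, and the percentages of benefit also rest on an assumed brace effect that the Protocol does not give. An analyst would report the difference with its confidence interval, treat Velcro's benefit as an assumption, and not present similar scores as proof that either fastening controls symptoms. That is ordinary care in interpretation. Whether a small validation study of a fastening should also re-establish that the brace works is a design preference on which reasonable statisticians would differ.
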